9.2.4 Evaluation of Patient Sample

Before finalizing the study sample, Optum will assess the sample to determine the number of patients excluded and remaining due to the exclusion criterion that requires patients to have no new antihyperglycemic medications other than linagliptin on the index date.

If this evaluation shows that the study sample size would be negatively impacted by excluding these patients, patients with new antihyperglycemic medications on the index date will be kept in the sample and a binary variable will be created to flag the patients for further subanalysis.

9.3 VARIABLES

9.3.1 Exposures

An exposure variable will not need to be created for this study since all the study patients will have linagliptin exposure on the index date.

9.3.2 Outcomes

All outcomes will be measured in the follow-up period.

9.3.2.1 Primary outcomes

The primary outcome variable, change in HbA1c, as defined below, will be evaluated among the overall study sample and stratified across pre-defined age and renal function categories. Age categories will be defined as: 40 to 54 years, 55 to 64 years, 65 to 74 years, and ≥ 75 years. Renal function categories will be defined based on eGFR, calculated using the Chronic Kidney Disease Epidemiology Collaboration (CKD-EPI) equation (17), and categorized as: < 30 ml/min/1.73m², 30 to 44 ml/min/1.73m², 45 to 59 ml/min/1.73m², 60 to 89 ml/min/1.73m², and ≥ 90 ml/min/1.73m².

The HbA1c variable definitions assume that the majority of patients will have only one HbA1c measure during the follow-up period because providers are not likely to perform multiple HbA1c tests during a 180-day period. However, if this assumption turns out to be false after examining the data, Section 9.7.3 defines alternative analyses that will be conducted.

- **Change in HbA1c**—The change in HbA1c will be calculated for each patient by subtracting the patient's last (most recent) HbA1c value during the pre-index period (including the index date) from the patient's last (most recent) HbA1c value 60 to 180 days after the index date.
- **Follow-up HbA1c**—Follow-up HbA1c will be defined as the last (most recent) HbA1c value 60 to 180 days after the index date. The number of days from the index date to the last (most recent) HbA1c 60 to 180 days after the index date will also be recorded.

9.3.2.2 Secondary outcomes

The secondary outcome variable, HbA1c goal attainment, as defined below, will be evaluated among the overall study sample and stratified across pre-defined age and renal function categories. Age categories will be defined as: 40 to 54, 55 to 64, 65 to 74, and ≥ 75 years. Renal function categories will be defined based on eGFR as: < 30 ml/min/1.73m², 30 to 44 ml/min/1.73m², 45 to 59 ml/min/1.73m², 60-89 ml/min/1.73m², and ≥ 90 ml/min/1.73m².

- HbA1c goal attainment—A binary variable will be created to designate HbA1c goal attainment 60 to 180 days after the index date. HbA1c goal attainment will be defined as the presence of an HbA1c value $< 7.0\%$ any time 60 to 180 days after the index date.

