8. RESEARCH QUESTION AND OBJECTIVES

The purpose of this study is to assess glycemic control among adults with T2DM during the 60 to 180 days following initiation of linagliptin.

The primary study objective is to:

- Describe change in HbA1c among adults with T2DM within the 60 to 180 days following initiation of linagliptin across pre-defined age and renal function categories. Age categories will be defined as: 40 to 54 years, 55 to 64 years, 65 to 74 years, and ≥ 75 years. Renal function categories will be defined based on eGFR as: <30 ml/min/1.73m², 30 to 44 ml/min/1.73m², 45 to 59 ml/min/1.73m², 60 to 89 ml/min/1.73m², and ≥ 90 ml/min/1.73m².

The secondary study objectives are to:

- Compare change in HbA1c among adults with T2DM within 60 to 180 days following initiation of linagliptin across pre-defined age and renal function categories.
- Compare the proportion of adults with T2DM who achieve HbA1c $< 7.0\%$ within 60 to 180 days following initiation of linagliptin across the pre-defined age and renal function categories.

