9. RESEARCH METHODS

9.1 STUDY DESIGN

This will be a non-interventional cohort study using existing data from patients in the Optum Clinical Database which contains electronic health record (EHR) data from providers across the United States.

Real-world EHR data will be used to determine whether there is comparable effectiveness of linagliptin 5 mg daily on glycemic effectiveness as determined by the change in HbA1c and the percentage of patients achieving an HbA1c goal of < 7.0% during the 60 to 180 days after initiation of linagliptin across a range of age and renal function categories.

[figure not shown]

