9.2.2 Inclusion Criteria

To be included in the study sample, patients must meet all of the following criteria:

- ≥ 1 written prescription for linagliptin (Tradjenta[®], Jentaducto[®], or Jentaducto XR[®]) in the EHR data during the identification period (medication codes for index medications in Table 1 of [Annex 1, Appendix B](#))
- ≥ 40 years of age based on the year of the index date
- First active date in the EHR is ≥ 180 days prior to the index date
- ≥ 1 diagnosis code representing T2DM in the EHR data during the 180-day pre-index period or on the index date (diagnosis codes in Annex 1, Appendix A)
- ≥ 1 HbA1c value during the 180-day pre-index period or on the index date
- ≥ 1 HbA1c value 60 to 180 days after the index date

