- New antihyperglycemic medication on the index date – This variable will be created only if the evaluation of the patient sample described in Section 9.2.4 determines that, in order to preserve sample size, it is necessary to retain patients in the study if they have new antihyperglycemic medications other than linagliptin on the index date. A binary flag will be created to indicate whether or not the patient had ≥ 1 new antihyperglycemic medication other than linagliptin on the index date. A new antihyperglycemic medication will be defined as a written prescription or medication administration for any antihyperglycemic medication that was not present in the patient’s written prescription, medication administration, or medication history records during the pre-index period (based on the antihyperglycemic medication codes in Tables 2 through 13 of [Annex 1, Appendix B](#)). Individual antihyperglycemic medications will be distinguished by generic name using the column labelled “Medication Name” in Tables 2 through 13. Combination products containing two generic ingredients will be considered as two distinct antihyperglycemic medications. In addition, the specific new medications and medication classes on the index date will be captured and reported.
- Number of HbA1c values during the pre-index period (including the index date)—The number of HbA1c values each patient had during the pre-index period (including the index date) will be captured for each patient and categorized as follows: only 1 value, 2 values, or 3 or more values.
- Pre-index HbA1c value—The last (most recent) HbA1c value in the pre-index period (including the index date) will be captured and reported. The number of days from the last (most recent) pre-index HbA1c to the index date will also be recorded.
- Pre-index HbA1c category based on 8% threshold—The last (most recent) HbA1c value in the pre-index period (including the index date) will be used to categorize patients into one of the following categories: HbA1c < 8% or HbA1c \geq 8%.
- Pre-index HbA1c category based on 9% threshold—The last (most recent) HbA1c value in the pre-index period (including the index date) will be used to categorize patients into one of the following categories: HbA1c < 9% or HbA1c \geq 9%.
- Pre-index serum creatinine—The last (most recent) serum creatinine value in the pre-index period (including the index date) will be captured and reported.

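### HbA1c goal attainment counts patients who were already below 7.0% before linagliptin, so its comparison across age and eGFR groups can partly reflect starting position

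*Combined protocol and SAP*

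**What the plan says.** Section 8 sets as a secondary objective: "Compare the proportion of adults with T2DM who achieve HbA1c" below 7.0% after starting linagliptin, across the age and renal function categories. Section 9.1 uses "the percentage of patients achieving an HbA1c goal of < 7.0% during the 60 to 180 days after initiation of linagliptin", together with change in HbA1c, to judge whether effectiveness is comparable across those categories.

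Section 9.3.2.2 defines the endpoint. "A binary variable will be created to designate HbA1c goal attainment 60 to 180 days after the index date". The rule follows: "HbA1c goal attainment will be defined as the presence of an HbA1c value" under 7.0% at any point in that window. The population is also stated: "HbA1c goal attainment, as defined below, will be evaluated among the overall study sample and stratified across pre-defined age and renal function categories".

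On the baseline side, Section 9.2.2 requires at least one "HbA1c value during the 180-day pre-index period or on the index date". It names no level, and the exclusions in Section 9.2.3 do not mention HbA1c. Section 9.3.3.2 groups baseline values twice, once under "Pre-index HbA1c category based on 8% threshold" and once at 9%. It defines no group at 7%.

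Section 9.7.3 compares categorical measures by chi-square test. The multivariable model there, whose covariates include pre-index HbA1c, is for change in HbA1c and is only to be considered.

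**The concern.** To achieve a goal after starting a drug implies not having been there before. As written, a patient at 6.6% before the index date and 6.9% afterwards is an achiever although HbA1c rose. That follows from the definition and needs no assumption.

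Within one group, this blurs what the percentage means. Between groups, it can bias the comparison. If one age or eGFR category contains more patients already below 7.0%, it will show higher attainment with no better response. The effect can also run the other way and hide a real difference, which matters in a study that asks whether effectiveness is comparable. Section 7 notes that renal function often affects the choice of glucose-lowering agent. It is therefore plausible, though not stated, that some patients start linagliptin for renal reasons rather than for poor control, and that their share varies with eGFR.

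**Working it through.** **The plan's own figures.** Section 9.5 gives 92 per group (SD 1.2) and 143 per group (SD 1.5) for a 0.5% difference in mean change, 80% power, two-sided 0.05. A two-sample t-test calculation returns 92 and 143; the normal approximation returns 91 and 142. These figures are correct, but they concern change in HbA1c. None is given for goal attainment.

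**Model for the endpoint as written.** For one group let
- q = share below 7.0% before index,
- s = probability that such a patient has a follow-up value below 7.0%,
- r = probability that a patient starting at or above 7.0% has one.

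Then attainment = q·s + (1 − q)·r. Two groups A and B with the same s and r differ by (qB − qA)·(s − r). The documents give none of q, s or r, so every value below is an assumption.

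**Example, identical response.** s = 0.85, r = 0.25.
- q = 10%: 0.10 × 0.85 + 0.90 × 0.25 = 0.310.
- q = 25%: 0.25 × 0.85 + 0.75 × 0.25 = 0.400.

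The gap is 9 points. The share of achievers who were already at goal is 0.085/0.310 = 27% in the first group and 0.2125/0.400 = 53% in the second. With q of 5% and 15% the results are 0.280 and 0.340, a gap of 6 points.

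**Example, masked difference.** Keep the first group at 31%. The second group (q = 25%, s = 0.85) also shows 31% if r = (0.310 − 0.2125)/0.75 = 0.13. A contrast of 25% against 13% among those who could reach the goal would then appear as equality.

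**Range.** With s from 0.7 to 0.9, r from 0.2 to 0.3, and q of 5% v 15%, 10% v 20% or 10% v 30%:
- smallest gap: 0.10 × (0.7 − 0.3) = 4 points;
- largest gap: 0.20 × (0.9 − 0.2) = 14 points;
- share of achievers already at goal: 11% to 66%.

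**Chance that the test calls the gap significant** (two-sided 0.05, same scenarios): 84% to over 99% with 2,500 per group, and 10% to 71% with 143 per group. The 2,500 is the floor that Section 9.7.1 reports for the smallest age group at feasibility.

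**Does restriction to baseline 7.0% or above suffice?** Only if r is the same at every starting value. Take a mean change of −0.6 (assumed) and the protocol's SD of 1.2, with normally distributed change:
- from 7.5%: Φ((7.0 − 6.9)/1.2) = Φ(0.083) = 53%;
- from 9.0%: Φ((7.0 − 8.4)/1.2) = Φ(−1.167) = 12%.

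With SD 1.5 the figures are Φ(0.067) = 53% and Φ(−0.933) = 18%. Section 9.9 expects larger falls from higher baselines, which narrows this contrast. To close it, the mean fall from 9.0% would have to be 0.6 + 1.5 = 2.1 points. Restricted groups with different baselines above 7.0% would therefore still differ, and the model needs pre-index HbA1c as well.

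**The case against.** The strongest reply is that the gap shown is ordinary baseline confounding. In the example both groups have the same success rate within each baseline category, so stratifying or adjusting on the full sample would remove the gap without changing the denominator. That is right. A reader might infer a denominator defect that no adjustment could cure, but the arithmetic does not support this. What adjustment on the full sample leaves untouched is the label: patients already at goal are still counted as achieving it. The protocol, however, plans no adjustment for this endpoint.

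Second, the purpose stated in Section 8 is to assess glycemic control, Section 9.5 calls the study exploratory, and Section 9.3.2.2 names its population openly. The proportion below 7.0% among all initiators is a legitimate description of control. This stands, and is a reason to keep that figure under another name. It does not make the figure a measure of achievement or response.

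Third, pre-index characteristics are compared across strata, so an imbalance may be seen, and Section 9.9 recognises possible baseline HbA1c differences. Seeing an imbalance does not take it out of the endpoint, and Section 9.9 discusses it for change in HbA1c only.

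Fourth, a reader might infer that no planned table separates patients already at goal. That cannot be said. The table shells are in a separate analysis plan that was not available. What can be said is that the protocol text defines no 7% baseline category.

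Fifth, selecting on a single last value at or above 7.0% brings in regression to the mean near the cut-off. This also stands: the level of attainment after restriction should not be read as drug effect alone.

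**Conclusion.** The point holds as a proportionate improvement. It is certain from the text that patients below 7.0% before linagliptin are eligible and can count as achievers. It is also certain that the planned comparison of attainment is unadjusted.

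Bias between strata is conditional: it arises only if the share already at goal differs by age or eGFR category. A reader might infer that this difference is established, or that the spurious gap is known to be large. The documents support neither, since they give no baseline HbA1c distribution and Section 9.9 says only that baseline differences may exist. The 4 to 14 points and the significance probabilities rest wholly on assumed q, s and r. The 2,500 per group is a feasibility count reported before several of the final criteria are mentioned, and Section 9.7.1 gives no counts by eGFR category. If the shares at goal are similar across strata, the bias is negligible and only the label remains wrong.

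**What to change.** 1. In Section 9.3.3.2, add a pre-index HbA1c category of below 7.0% against 7.0% or above, from the same last pre-index value used for the 8% and 9% groups.
2. In Section 9.3.2.2, report for each age and eGFR category the number already below 7.0%, the share of them still below 7.0% at follow-up, and the share of those starting at 7.0% or above who reach below 7.0%.
3. In Section 9.7.3, base the between-strata comparison of achievement on patients starting at 7.0% or above, with a logistic model that includes pre-index HbA1c. Restriction alone leaves baseline differences above 7.0%.
4. Keep the overall proportion below 7.0% if wanted, labelled as glycemic control at follow-up. Change in HbA1c keeps the full sample.
5. Bring the table shells in the analysis plan into line.

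No new data are needed, because every included patient has a pre-index HbA1c. The cost is a smaller denominator for the achievement comparison and a lower headline percentage. Cell sizes after restriction should be checked, above all in the small eGFR categories.

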9.3.3 Covariates

Covariates will include demographic and clinical characteristic variables measured during the pre-index period (including the index date) unless otherwise noted.

9.3.3.1 Demographics

- Age—Age will be defined as of the index year.
- Age categories—Patients will be categorized to one of the following age groups:
 - 40 to 54 years
 - 55 to 64 years
 - 65 to 74 years
 - ≥ 75 years
- Sex—Sex will be captured and recorded.
- Race—Race will be categorized as follows:
 - White
 - African American (AA)
 - Asian
 - Other/ Unknown
- Ethnicity
 - Hispanic
 - Non-Hispanic
 - Unknown
 - Not Available

- Geographic region—The U.S. region will be determined and reported. States will be categorized into five geographic regions in accordance with the U.S. Census Bureau’s region designations as presented in the table below.

Table 1. United States Geographic Regions

Region	Division	State
Northeast	New England	CT, MA, ME, NH, RI, VT
	Mid Atlantic	NJ, NY, PA
Midwest	East North Central	IL, IN, MI, OH, WI
	West North Central	IA, KS, MN, MO, ND, NE, SD
South	South Atlantic	DC, DE, FL, GA, MD, NC, SC, VA, WV
	East South Central	AL, KY, MS, TN
	West South Central	AR, LA, OK, TX
West	Mountain	AZ, CO, ID, MT, NM, NV, UT, WY
	Pacific	AK, CA, HI, OR, WA
Other	Other	Armed Forces Americas (except Canada), Armed Forces (Europe, Canada, Middle East, Africa), Armed Forces Pacific, American Samoa, Federated State of Micronesia, Guam, Marshall Islands, Commonwealth of the Northern Mariana Islands, Puerto Rico, Palau, Virgin Islands

9.3.3.2 Clinical Characteristics

- Pre-index Quan-Charlson comorbidity score—Quan-Charlson comorbidity score will be calculated based on the presence of diagnosis codes in the pre-index period (including the index date) (16). The Quan-Charlson comorbidity score will also be categorized into the following groups: zero, one to two, three to four, and five or more.
- Pre-index comorbid conditions-General comorbid conditions will be defined using the Clinical Classifications Software managed by the Agency for Healthcare Research and Quality (AHRQ) (17). This measure generates indicator variables for specific disease conditions based on diagnosis codes. The top 20 comorbid conditions will be presented.
- Pre-index antihyperglycemic medications— Pre-index antihyperglycemic medications will be identified based on written prescription, medication administration, and medication history records in the EHR data during the pre-index period. Binary flags, one per medication class and another per distinct medication based on generic name, will be created for the antihyperglycemic medications. Medication classes will be determined using the “Medication Class” column in Tables 2 through 13 of [Annex 1, Appendix B](#) and will include metformin, sulfonylureas, meglitinides, thiazolidinediones (TZDs), DPP-4 inhibitors other than linagliptin, glucagon-like peptide-1 receptor agonists (GLP-1RA), sodium-glucose co-transporter 2 (SGLT2) inhibitors, basal insulins, bolus insulins, mixed insulins, alpha glucosidase inhibitors, and amylin analogs. Combination products containing two medication classes will be considered as two distinct medication classes. Distinct medications will be determined using the “Medication Name” column in Tables 2 through 13 of [Annex 1, Appendix B](#). Combination products containing two generic ingredients will be considered as two distinct antihyperglycemic medications.

- Pre-index antihyperglycemic therapy categories—Patients will be categorized into one of the following groups based on the medication class for their pre-index antihyperglycemic therapies:
 - Metformin only
 - Sulfonylurea only
 - Meglitinide only
 - TZD only
 - GLP-1RA only
 - SGLT2 inhibitor only
 - Basal insulin only
 - Metformin + sulfonylurea
 - Other combination (additional groups will be created for any medication class combinations that are present among least 5% of the study sample)
- New antihyperglycemic medication on the index date – This variable will be created only if the evaluation of the patient sample described in Section 9.2.4 determines that, in order to preserve sample size, it is necessary to retain patients in the study if they have new antihyperglycemic medications other than linagliptin on the index date. A binary flag will be created to indicate whether or not the patient had ≥ 1 new antihyperglycemic medication other than linagliptin on the index date. A new antihyperglycemic medication will be defined as a written prescription or medication administration for any antihyperglycemic medication that was not present in the patient’s written prescription, medication administration, or medication history records during the pre-index period (based on the antihyperglycemic medication codes in Tables 2 through 13 of [Annex 1, Appendix B](#)). Individual antihyperglycemic medications will be distinguished by generic name using the column labelled “Medication Name” in Tables 2 through 13. Combination products containing two generic ingredients will be considered as two distinct antihyperglycemic medications. In addition, the specific new medications and medication classes on the index date will be captured and reported.
- Number of HbA1c values during the pre-index period (including the index date)—The number of HbA1c values each patient had during the pre-index period (including the index date) will be captured for each patient and categorized as follows: only 1 value, 2 values, or 3 or more values.
- Pre-index HbA1c value—The last (most recent) HbA1c value in the pre-index period (including the index date) will be captured and reported. The number of days from the last (most recent) pre-index HbA1c to the index date will also be recorded.
- Pre-index HbA1c category based on 8% threshold—The last (most recent) HbA1c value in the pre-index period (including the index date) will be used to categorize patients into one of the following categories: HbA1c < 8% or HbA1c \geq 8%.
- Pre-index HbA1c category based on 9% threshold—The last (most recent) HbA1c value in the pre-index period (including the index date) will be used to categorize patients into one of the following categories: HbA1c < 9% or HbA1c \geq 9%.
- Pre-index serum creatinine—The last (most recent) serum creatinine value in the pre-index period (including the index date) will be captured and reported.
- Pre-index renal function—Pre-index renal function will be assessed using estimated glomerular filtration rate (eGFR) which will be calculated using the Chronic Kidney Disease Epidemiology Collaboration (CKD-EPI) equation (18). This equation

requires variables for serum creatinine, age, sex, and race but weight and height are not required because the results are normalized to 1.73 m² body surface area (an accepted average adult surface area) (19). The last (most recent) serum creatinine value in the pre-index period (including the index date) will be used for the serum creatinine (Scr) variable. The CKD-EPI equation (18) to estimate GFR in units of ml/min/1.73m² after incorporating multiplication factors for race and sex into the intercept is displayed in [Table 2](#). For purposes of this eGFR calculation, race will be categorized as either AA or non-AA (includes White, Asian and Other/Unknown).

Table 2. CKD-EPI equation (Adapted from Reference 18)

Race	Sex	Scr (mg/dL)	Equation for eGFR in units of ml/min/1.73m ²
AA	Female	≤ 0.7	$eGFR = 166 \times \left(\frac{Scr}{0.7}\right)^{-0.329} \times (0.993)^{Age}$
AA	Female	> 0.7	$eGFR = 166 \times \left(\frac{Scr}{0.7}\right)^{-1.209} \times (0.993)^{Age}$
AA	Male	≤ 0.9	$eGFR = 163 \times \left(\frac{Scr}{0.9}\right)^{-0.411} \times (0.993)^{Age}$
AA	Male	> 0.9	$eGFR = 163 \times \left(\frac{Scr}{0.9}\right)^{-1.209} \times (0.993)^{Age}$
Non-AA	Female	≤ 0.7	$eGFR = 144 \times \left(\frac{Scr}{0.7}\right)^{-0.329} \times (0.993)^{Age}$
Non-AA	Female	> 0.7	$eGFR = 144 \times \left(\frac{Scr}{0.7}\right)^{-1.209} \times (0.993)^{Age}$
Non-AA	Male	≤ 0.9	$eGFR = 141 \times \left(\frac{Scr}{0.9}\right)^{-0.411} \times (0.993)^{Age}$
Non-AA	Male	>0.9	$GFR = 141 \times \left(\frac{Scr}{0.9}\right)^{-1.209} \times (0.993)^{Age}$

- Pre-index renal function categories—Patients will be categorized into one of the following renal function groups based on their eGFR during the pre-index period (including the index date):
 - < 30 ml/min/1.73m²
 - 30 to 44 ml/min/1.73m²
 - 45 to 59 ml/min/1.73m²
 - 60 to 89 ml/min/1.73m²
 - ≥ 90 ml/min/1.73m²
 - Not available

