9.2.3 Exclusion Criteria

Patients will be excluded from the study sample if they have any of the following:

- ≥ 1 written prescription, medication administration or medication history record for linagliptin or other DPP-4 inhibitor in the EHR data during the 180-day pre-index period (medication codes for DPP-4 inhibitors in Table 2 of [Annex 1, Appendix B](#))
- ≥ 1 written prescription or medication administration for a new antihyperglycemic medication other than linagliptin on the index date

New antihyperglycemic medication will be defined as a written prescription or medication administration for any antihyperglycemic medication that was not present in the patient's written prescription, medication administration, or medication history records during the 180-day pre-index period. Medication codes for antihyperglycemic medications are shown in Tables 2 through 13 of [Annex 1, Appendix B](#). Individual antihyperglycemic medications will be distinguished by generic name using the column labelled "Medication Name" in Tables 2 through 13. Combination products containing two generic ingredients will be considered as two distinct antihyperglycemic medications.

Note: This exclusion criterion is designed to exclude patients from the study sample if they start a new antihyperglycemic medication other than linagliptin on the index date. Patients that start a new antihyperglycemic medication in the follow-up period will not be removed from the study sample to avoid creating a biased sample. Addition of a new antihyperglycemic medication during follow-up will be evaluated through the sensitivity analysis described in Section 9.7.4.4. While we will be capturing additions of new therapies, discontinuation of linagliptin is not able to be accurately measured in electronic record data. The electronic record data capture prescriptions written by a prescriber, but it is not possible to know if patients received and adhered to their medication and there are no structured data fields to identify if and when a medication was discontinued by the patient or the provider.

- ≥ 1 diagnosis code or procedure code representing renal transplant, solid organ transplant, or bone marrow transplant in the EHR data during the 180-day pre-index period or on the index date (diagnosis and procedure codes in [Annex 1, Appendix A](#))

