9.7.3 Secondary Analysis

For the secondary analysis, results will be stratified by age, renal function, and race/ethnicity. Comparisons of pre-index characteristics and outcome measures across age, renal function, and race/ethnicity strata will be provided, and appropriate tests will be used based on the distribution of the measure. Continuous measures will be compared using t-tests and categorical measures will be compared using chi-square tests. P-values and 95% confidence intervals will be reported. Reported p-values will not be adjusted for multiple comparisons.

In addition, as part of the secondary analysis, multivariable modelling will be considered to assess change in HbA1c, controlling for an a priori list of covariates. The use of multivariable modelling will be dependent on having robust sample size distribution (as defined in Section 9.5 Study Size) across age and eGFR categories.

Since the primary outcome of change in HbA1c is calculated using just two timepoints, pre-index and follow-up, multivariable analysis will be conducted using ordinary least squares (OLS). In the event that the assumption that the majority of patients have only one HbA1c measure during the follow-up period turns out to be false and there are multiple HbA1c values per patient during this timeframe, mixed models repeated measures (MMRM) will be used to control for the correlation of multiple HbA1c observations from the same patient.

Following standard procedure, regression diagnostics will be performed for each model to assess goodness of fit and violations of model assumptions (e.g., multicollinearity,

heteroskedasticity). When there are violations of the model, Optum will note them and make appropriate corrections to the data (i.e., typically through transformation of either the independent or dependent variables) or in the method of estimation.

The following list of covariates will be included in the model provided sufficient sample size distribution:

- Age categories (40 to 54 years, 55 to 64 years, 65 to 74 years, and ≥ 75 years)
- Sex
- Race
- Ethnicity
- Geographic region
- Pre-index HbA1c
- Pre-index renal function categories based on eGFR (< 30 ml/min/1.73m², 30 to 44 ml/min/1.73m², 45 to 59 ml/min/1.73m², 60 to 89 ml/min/1.73m², and ≥ 90 ml/min/1.73m²)
- Pre-index Quan-Charlson comorbidity score

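### An antihyperglycemic started between the baseline HbA1c and the index date is neither excluded nor adjusted for, and the recorded HbA1c intervals are missing from the Section 9.7.3 model

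*Combined protocol and SAP*

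**What the plan says.** Section 9.2.2 requires at least one "HbA1c value during the 180-day pre-index period or on the index date", and Section 9.3.2.1 takes the most recent such value as baseline. On the other side of index, "Follow-up HbA1c will be defined as the last (most recent) HbA1c value 60 to 180 days after the index date".

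Both intervals are captured. Section 9.3.3.2 says "The number of days from the last (most recent) pre-index HbA1c to the index date will also be recorded", and Section 9.3.2.1 also records "The number of days from the index date to the last (most recent) HbA1c 60 to 180 days after the index date".

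On co-medication, Section 9.2.3 drops patients "if they start a new antihyperglycemic medication other than linagliptin on the index date". A drug is new only if it is absent from the patient's "written prescription, medication administration, or medication history records during the 180-day pre-index period". Any linagliptin or other DPP-4 inhibitor record in those 180 days is a separate exclusion. Drugs added during follow-up are assigned to a sensitivity analysis in Section 9.7.4.4, which is not in the text available for review.

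Section 9.7.3 introduces its model with "The following list of covariates will be included in the model provided sufficient sample size distribution". The list is age category, sex, race, ethnicity, region, pre-index HbA1c, eGFR category, Quan-Charlson score and individual comorbidities. It has no interval and no drug variable, although Section 9.3.3.2 builds pre-index drug flags and therapy categories.

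**The concern.** The change score is meant to show what happened after linagliptin was started. If the baseline HbA1c is months old and another glucose-lowering drug was started in between, the score carries both effects. The plan already treats this kind of contamination as important on the index date, where it excludes, and during follow-up, where it promises a sensitivity analysis. The gap between baseline HbA1c and index has no such protection, and Sections 9.9 and 9.12 do not list it as a limitation.

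Section 9.1 asks whether effectiveness is comparable across age and renal function. If gap starts or measurement timing vary by stratum, part of an observed difference would have nothing to do with age or eGFR. The same mechanism could also hide a true difference and support a claim of comparability that is not warranted.

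**Working it through.** **1. The plan's own figures.** Section 9.5 gives 92 and 143 per group for a 0.5% difference, 80% power, two-sided alpha 0.05, and SD 1.2 or 1.5. A two-sample t-test calculation gives 91.4, rounded up to 92, and 142.2, rounded up to 143. Both reproduce, and nothing below changes them.

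**2. Spacing allowed by the windows.** The shortest interval between the two HbA1c values is 0 + 60 = 60 days. The longest is 180 + 180 = 360 days.

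**3. One patient traced through the rules (hypothetical).** Baseline HbA1c falls on day -120, a non-DPP-4 antihyperglycemic is first recorded on day -60, linagliptin is prescribed on day 0, and follow-up HbA1c falls on day 150.
- Section 9.2.3: the drug has a pre-index record, so it is not new and the patient is kept.
- Section 9.3.3.2: the drug raises an ordinary pre-index flag, not dated against the baseline HbA1c.
- Section 9.7.3: neither that flag nor the 120-day interval enters the model.
- The change from day -120 to day 150 is read as change after linagliptin. Pre-index HbA1c is a covariate, but it was measured before the drug was started and cannot correct for it.

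**4. Size of a gap-start bias.** Bias in a contrast = (difference between strata in the share with a gap start) × (effect of that drug on the change). Assumed inputs: a difference of 10 to 20 points, and an effect of 0.64 to 0.77%. The effect range borrows the placebo-adjusted linagliptin results in Section 7 as a stand-in for an unnamed drug.
- Low: 0.10 × 0.64 = 0.064%.
- High: 0.20 × 0.77 = 0.154%.

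**5. Size of a follow-up timing bias.** Assume the effect E is approached exponentially with time constant τ of 30 to 60 days. The shortfall at day t is then E·exp(-t/τ). Suppose follow-up is spread evenly over days 60 to 160 in one stratum and days 80 to 180 in another, a 20-day mean shift. The mean of exp(-t/τ) over days a to b is τ[exp(-a/τ) - exp(-b/τ)]/(b - a).
- τ = 30, E = 0.64: 0.64 × (0.0392 - 0.0201) = 0.012%.
- τ = 60, E = 0.77: 0.77 × (0.1790 - 0.1283) = 0.039%.

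**6. Against the study's precision.** Section 9.7.1 reports more than 2,500 patients in the smallest age group. That is a feasibility count with slightly different windows, so the final number will differ. SE = SD × √(2/n).

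| n per group | SD | SE | Difference detectable at 80% power | Chance of p < 0.05 with no true difference, at bias 0.064 / 0.154 |
|---|---|---|---|---|
| 2,500 | 1.5 | 0.042 | 0.12 | 33% / 95% |
| 2,500 | 1.2 | 0.034 | 0.10 | 47% / 99% |
| 143 | 1.5 | 0.177 | 0.50 | 6% / 14% |

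The documents give no eGFR group sizes, so those contrasts could lie anywhere in this range.

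**The case against.** A reader might infer that the plan makes no use of the intervals. The text does not support that. Section 9.7.2 has the study variables described overall and by stratum, and Section 9.7.3 compares pre-index and outcome measures between strata. Both intervals would probably be tabulated, so an imbalance could be seen. What stands is that they are absent from the model.

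A reader might also compare a value at day 60 with one at day 180. On the curve in the working, that gap is 0.64 × (exp(-2) - exp(-6)) = 0.09% to 0.77 × (exp(-1) - exp(-3)) = 0.24%. It is a contrast between two single measurements. It would be a stratum bias only if one stratum were tested entirely at day 60 and another entirely at day 180. Section 9.9 says only that the maximum is usually reached by 6 months, not how far short day 60 falls.

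It is fair to add that the share difference, drug effect and time constants are all assumed, that 0.06 to 0.15% is well below the 0.5% used for sizing, and that the model is only to be considered, within an exploratory study. These points limit severity. They do not close the gap, because with thousands of patients per age group small biases reach nominal significance.

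Two cautions about remedies also stand. Only 180 days of look-back are guaranteed. With a baseline HbA1c on day -150, just 30 days remain in which to find earlier use, so a renewal can look like a start. And follow-up timing is measured after index and may depend on response, so routine adjustment for it could itself introduce bias.

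Finally, Section 9.7.4.4 and the separate analysis plan cited for table shells cannot be checked here. As described in Section 9.2.3, the 9.7.4.4 analysis covers additions during follow-up, not gap starts. If most patients have several follow-up values, a repeated-measures model replaces OLS, but no time term is stated and it would not address events before index.

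**Conclusion.** The gap is real. A non-DPP-4 antihyperglycemic started after the baseline HbA1c and before index passes the exclusion, is not in the model, and has its effect counted as change after linagliptin. The overall descriptive change is affected wherever such starts occur.

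It would be too strong to say that the age or eGFR contrasts are biased. That requires the age of the baseline value, gap starts or follow-up timing to differ by stratum, and the documents give no data on any of these. Under the assumptions stated in the working, gap starts could shift a contrast by 0.06 to 0.15% and a 20-day timing difference by about 0.01 to 0.04%. Gap starts are therefore the main issue and follow-up timing a minor one. This should be corrected because the correction is cheap; it does not undermine the design.

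**What to change.** 1. Add days from baseline HbA1c to index to the Section 9.7.3 covariates.
2. State explicitly that both intervals will be reported by age and eGFR stratum.
3. Add a sensitivity analysis of change in HbA1c by stratum, descriptive and modelled. Restrict it to patients whose baseline HbA1c is within 90 days of index and who have no antihyperglycemic first recorded between that value and index. Use all available earlier records, not only the 180-day window, to separate starts from renewals.
4. Adjust for days from index to follow-up HbA1c only as a sensitivity analysis, showing results with and without it.

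Leave the eligibility windows unchanged.

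The cost is protocol wording, one covariate that is already recorded, and a modest amount of programming from the medication records in use. No patients are lost from the main analysis. The restricted analysis will be smaller, and some starts will still be misclassified where no record exists before the guaranteed 180 days. The main descriptive results and t-tests remain unadjusted, so the restricted analysis is the check on those.
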